8.1. Administrative and General/Baseline Procedures

The baseline visit will occur on the same day as the EoTP visit of ARGX-113-2009. All baseline assessments will be performed before administration of efgartigimod PH20 SC. Assessments do not need to be repeated if they are performed as part of ARGX-113-2009.

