2. GENERAL METHODOLOGY

2.1 ANALYSIS SETS

2.1.1 *Analysis sets*

The following participant analysis sets (PAS) will be used:

Rollover (ROL) analysis set: All participants who rolled over from ARGX-113-2009 and provided informed consent for participation in ARGX-113-2010

Safety (SAF) analysis set: All participants from the ROL analysis set who received at least one dose of IMP

Notes:

- Provided informed consent is defined as having a complete informed consent signature date in the database.
- Received at least one dose of IMP is defined as having an exposure date or any information confirming exposure present in the database.

2.1.2 *As planned versus as actual analysis*

Not applicable. All endpoints will be analyzed for the total group of participants, regardless of previous treatment in ARGX-113-2009 (placebo or efgartigimod PH20 SC).

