2.2 PHASES, PERIODS AND TIME POINTS

2.2.1 *Analysis phases, periods and subperiods*

All assessments and events will be allocated to analysis phases, periods and subperiods as defined in below table.

Table 2: Analysis phase, period and subperiod definition

Phase	Period/Subperiod	Start	End
For participants who don't receive the first IMP administration at the ARGX-113-2010 baseline visit^a, the first phase will be the observation phase.			
For participants who receive the first IMP administration at the ARGX-113-2010 baseline visit^a, the first phase will be the treatment phase.			
Observation		Date of baseline visit in ARGX-113-2010, with 00:00 added as time part	
For participants with a subsequent treatment period:
 
First IMP administration date/time – 1 minute.
 
For other participants:
 
Date of week 48 or EDV visit^c, with 23:59 added as time part.
 
For participants who don't have a week 48 or EDV visit: date of last contact, with 23:59 added as time part.

	Statistical Analysis Plan	
ARGX-113-2010	Final analysis	Final 1.0 of 29APR2025

Phase	Period/Subperiod	Start	End
Treatment	Treatment period 1/ On IMP treatment	
For participants with first IMP administration at the baseline visit:
 
Date of baseline visit in ARGX-113-2010, with 00:00 added as time part.
 
For participants with a previous observation phase and who initiate treatment:
 
First IMP administration date/time
	
For participants with a subsequent Off IMP subperiod:
 
Last IMP administration date/time in treatment period 1.
 
For other participants:
 
Date of week 48 or EDV visit^c, with 23:59 added as time part.
 
For participants who don't have a week 48 or EDV visit: date of last contact, with 23:59 added as time part.

	Treatment period 1/ Off IMP treatment	Last IMP administration date/time in treatment period 1 + 1 minute	
For participants with a subsequent treatment period:
 
First IMP administration date/time in next treatment period – 1 minute.
 
For other participants:
 
Date of week 48 or EDV visit^c, with 23:59 added as time part.
 
For participants who don't have a week 48 or EDV visit: date of last contact, with 23:59 added as time part.

Treatment period 2 is applicable for participants who re-initiate IMP administration after a previous Off IMP subperiod^b.			

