3.2 DEMOGRAPHIC AND OTHER BASELINE CHARACTERISTICS

3.2.1 *Available data*

The following parameters will be available:

- Demographics: sex at study start, childbearing potential, year of birth, age at informed consent, race, ethnicity, height, body weight and BMI at study baseline, date of signing ICF
- Baseline disease characteristics: disease status at study baseline (no CDA, CDA, CR, PR, Relapse, Treatment failure), BPDAl activity and total score at study baseline, IGA-BP at study baseline, itch NRS 24-hour average and worst score at study baseline

	Statistical Analysis Plan	
ARGX-113-2010	Final analysis	Final 1.0 of 29APR2025

- Study entry status: date of protocol version at entry, participant receiving rescue therapy at study baseline (yes, no), type of rescue therapy at study baseline (ATC class level 3), participant receiving OCS at study baseline (yes, no), and if yes, OCS dose at study baseline (mg) and OCS dose per body weight at study baseline (mg/kg)

3.2.2 *Derivation rules*

The following parameters will be derived:

- Age at informed consent, categorized (18 - <65, 65 - <75, 75 - <85, >=85)
- Height: if height is not available in the database of ARGX-113-2010, the height at screening of ARGX-113-2009 will be taken.
- BMI at study baseline (kg/m²) = (body weight (kg) at study baseline) / (height (m))².
- BMI at study baseline, categorized (Underweight: < 18.5 kg/m², Normal weight: 18.5 -< 25 kg/m², Overweight: 25 -< 30 kg/m², Obese: >= 30 kg/m²)
- Race, categorized (Asian, Black or African American, White, Other)
- Geographical region: Asia (Japan, China), North America (US, Canada), EU region+UK (EU/EEA/EFTA/UK), Rest of world
- BPDAl activity score at study baseline, categorized: <20, 20-56, >56
- OCS at study baseline: any use of systemic OCS on study day 1, i.e.. any record from any eCRF page with medication class = 'GLUCOCORTICOIDs' and route = 'ORAL' for which the available information indicates that the medication is taken on study day 1.
- Rescue therapy at study baseline: any use of therapy that is indicated as rescue therapy by the investigator on the eCRF page and for which the available information indicates that the medication is taken on study day 1.

3.2.3 *Presentation of results*

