4. EFFICACY, PHARMACODYNAMIC, AND IMMUNOGENICITY ANALYSES

4.1 EFFICACY AND QUALITY OF LIFE

All efficacy endpoints are secondary endpoints in this OLE study and will be evaluated descriptively.

4.1.1 *Available data*

Investigators report the participant's best disease status in episodes with start and end date (no CDA, CDA, CR, PR, Relapse and Treatment failure). Furthermore, BPDAI activity and total score, IGA-BP scores and itch NRS are collected over time.

Quality of life is assessed over time using the ABQOL, DLQI and EQ-5D-5L questionnaires.

The health impact of long-term glucocorticoid use is assessed via the Aggregate Improvement Score (AIS) and Cumulative Worsening Score from the Glucocorticoid Toxicity Index (GTI) and via the GTI Specific List (GTI-SL).

4.1.2 *Derivation rules*

The following endpoints will be derived **for each treatment period separately**:

- 1) Participants achieving CR while off OCS for ≥ 8 weeks (CROff). A participant will be considered a CROff responder if the following criteria are met simultaneously for ≥ 8 weeks (56 days):
 - The participant's reported disease status is CR
 - The participant is off OCS therapy
 - The participant does not receive any rescue therapy (as indicated by the investigator on the eCRF)

Else, the participant will be considered a CROff non-responder. Participants who already have the disease status CR at day 1 of the treatment period or who are off OCS therapy at day 1 of the treatment period or who receive rescue therapy at day 1 of the treatment period, will be considered non-evaluable for this endpoint and will be excluded from this analysis for the corresponding treatment period.

Note: the rules for assessing the OCS dose on a given day are described in section 3.4.2. Similarly, these rules can be used to assess whether rescue therapy is received on a given day. Additionally for rescue therapy, a frequency of PRN (pro re nata, or 'as needed') will be interpreted as a dose of 1 time per week.

- 2) Participants achieving CR or PR while off OCS for ≥ 8 weeks (CR/PROff). A participant will be considered a CR/PROff responder if the following criteria are met simultaneously for ≥ 8 weeks (56 days):
 - The participant's reported disease status is CR or PR (continuously or alternately)
 - The participant is off OCS therapy
 - The participant does not receive any rescue therapy (as indicated by the investigator on the eCRF)

	Statistical Analysis Plan	

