Else, the participant will be considered a non-responder for CROff without IMP. Participants who enter the ARGX-113-2010 study under protocol version 3 (26 April 2024) or 4 (02 May 2024) will be considered non-evaluable for this endpoint. Furthermore, participants who were randomized to the placebo arm in the ARGX-113-2009 study and who enter the ARGX-113-2010 study in the observation phase, will be considered non-evaluable for this endpoint in the observation phase.

- 6) Participants achieving CR or PR while off both OCS and efgartigimod PH20 SC for ≥ 8 weeks (CR/PROff without IMP). A participant will be considered a

	Statistical Analysis Plan	
ARGX-113-2010	Final analysis	Final 1.0 of 29APR2025

responder for CR/PROff without IMP if the following criteria are met simultaneously for ≥ 8 weeks (56 days):

- The participant's reported disease status is CR or PR (continuously or alternately)
- The participant is off OCS therapy
- The participant is off IMP
- The participant does not receive any rescue therapy (as indicated by the investigator on the eCRF)

Else, the participant will be considered a non-responder for CR/PROff without IMP. A participant will be considered non-evaluable for this endpoint using the same rules as for CROff without IMP.

- 7) Duration of sustained remission will be calculated for participants achieving CR while off both OCS and efgartigimod PH20 SC for ≥ 8 weeks (i.e., responders for CROff without IMP) within a treatment period.
 - Start date of sustained remission is 1 week (7 days) after the last IMP administration in the treatment period
 - End date of sustained remission is:
 - the start date of first relapse after achieving CROff without IMP
 - the start date of a (next) treatment period
 - the start date of OCS therapy after achieving CROff without IMP
 - the start date of a rescue therapy after achieving CROff without IMP
 whichever comes first. If none of the above occurs, the participant will be censored at the end date of the study (end date of last phase).
 - Duration of sustained remission (in days) = end date - start date + 1
- 8) Relapse will be evaluated for participants having or achieving CDA, CR or PR during the treatment period (or observation phase). The evaluation period for relapse is till the end of the treatment period (or observation phase) in case a (next) treatment period starts, or else till the end of the study. Only the first relapse in a treatment period (or observation phase) will be considered.

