- 9) Time to relapse:
 - Start date is the first day with status CDA, CR or PR in the treatment period (or observation phase)
 - End date is:
 - the start date of first relapse after having or achieving CDA, CR or PR
 - the end date of the study (end date of last phase), if no relapse
 - Time to relapse (in days) = end date - start date + 1
- 10) For participants with relapse, severity of (first) relapse will be calculated as the BPDAl total score at the onset of relapse (use the first available nonmissing BPDAl total score in the interval of relapse) minus the BPDAl total score at the preceding visit (use the most recent preceding visit for which a nonmissing BPDAl total score is available). Severity of relapse will be categorized as <0 , $0- <10$, $10- <20$, $20- <30$, or >30 .

	Statistical Analysis Plan	
ARGX-113-2010	Final analysis	Final 1.0 of 29APR2025

The following endpoints will be derived **overall**:

- 11) Changes and percent changes from study baseline will be calculated for BPDAI activity and total score.
- 12) Changes from study baseline will be calculated for itch NRS 24-hour average and worst scores.
- 13) C-GTI: Composite Glucocorticoid Toxicity Index comprises the Aggregate Improvement Score (AIS) and the Cumulative Worsening Score (CWS). Details of AIS and CWS derivations are specified in appendix 9.1.
- 14) A total ABQOL score is calculated as the sum of all 17 items score 0 to 3 with higher score indicating worse condition. Missing items are imputed with the average score of the present items if at least half (9) of the items are present. The total score is rounded to the highest integer.
- 15) Changes from study baseline will be calculated for EQ-5D-5L VAS score, DLQI score and total ABQOL score.

4.1.3 *Presentation of results*

Efficacy results will be presented for the ROL analysis set, unless mentioned otherwise. For tables by analysis visit, only the study baseline and last assessment analysis visits will be shown. Other analysis visits will be included in listings.

A frequency tabulation will be created for the number and percentage of participants who achieved CROff at least once during the study (i.e., in any treatment period). The table will also present the number of participants who are evaluable for the endpoint at least once during the study. This number will serve as denominator for the percentage calculation. This table will be based on the SAF analysis set.

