Similar frequency tabulations will be created for the number and percentage of participants who achieved:

- CR/PROff
- CRmin
- Treatment failure

Similar frequency tabulations, based on the ROL analysis set, will be created for:

- CROff without IMP
- CR/PROff without IMP
- Relapse

Duration of sustained remission and time to relapse will be descriptively presented with median times, quantiles and number and percentage of censored observations and observations with event. Only the participant's first evaluation during the study will be included as observation.

Duration of sustained remission will be presented for the SAF analysis set.

A frequency tabulation will be created for categorized severity of relapse, for the participant's first relapse during the study.

	Statistical Analysis Plan	
ARGX-113-2010	Final analysis	Final 1.0 of 29APR2025

Descriptive statistics will present the actual values, changes and percent changes from study baseline of the BPDAl activity and total scores per analysis visit (baseline and last assessment).

Frequency tabulations will be provided for the outcome of IGA-BP per analysis visit (baseline and last assessment). Additionally, cumulative percentages (starting with the best outcome result) will be calculated.

Descriptive statistics will present the actual values and changes from study baseline of the itch NRS 24-hour average and worst scores per analysis visit (baseline and last assessment).

Descriptive statistics will be provided for the C-GTI scores AIS and CWS at the last assessment.

Frequency tabulations will be provided for the outcomes of the ABQOL (17 items), EQ-5D-5L (5 dimensions) and DLQI (10 items), similar to the frequency tabulations of the IGA-BP outcomes. Descriptive statistics on absolute values and changes from study baseline for EQ-5D-5L VAS score, DLQI score and Total ABQOL score will be calculated per analysis visit (baseline and last assessment), similar to the descriptive statistics of the itch NRS scores.

Listings will be created for:

- Disease status, including the derived response variables (CROff, CR/PROff, CRmin, etc.)
- Duration of sustained remission and time to relapse, including the reason for censoring (if applicable) and the severity of relapse
- Lesion assessments
- BPDAl assessments
- IGA-BP assessments
- Itch NRS assessment
- Calculated C-GTI scores and complementary GTI specific list (GTI-SL)
- ABQOL, EQ-5D-5L and DLQI data

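### Time to relapse runs from rollover for participants already in control and from onset for the others, and one Kaplan-Meier table pools both, so its median has no single meaning

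*SAP*

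**What the plan says.** SAP section 4.1.2 item 8 sets who is evaluated: "Relapse will be evaluated for participants having or achieving CDA, CR or PR during the treatment period (or observation phase". Item 9 sets the clock: "Start date is the first day with status CDA, CR or PR in the treatment period (or observation phase". The end date is the first relapse after that or, without relapse, the end of the study.

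SAP Table 2 starts the first phase, whether observation or treatment, at "Date of baseline visit in ARGX-113-2010, with 00:00 added as time part". Protocol section 8.1 fixes that day: "The baseline visit will occur on the same day as the EoTP visit of ARGX-113-2009".

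SAP section 3.2.1 lists among the available data "disease status at study baseline (no CDA, CDA, CR, PR, Relapse, Treatment failure", so participants already in CDA, CR or PR at entry are foreseen. Section 4.1.1 says that investigators report each participant's "best disease status in episodes with start and end date".

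On presentation, section 4.1.3 specifies medians, quantiles and censoring counts. It adds that only the participant's "first evaluation during the study will be included as observation". Section 2.1.2 states: "All endpoints will be analyzed for the total group of participants, regardless of previous treatment in ARGX-113-2009 (placebo or efgartigimod PH20 SC". Table 14.2.1.8 is a single Kaplan-Meier table on the rollover set, which section 2.4.2 presents under one Total label. No split by status at entry, delayed entry or sensitivity analysis is planned.

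**The concern.** A time-to-event curve is readable when everyone's clock starts at the same kind of moment. Here it does not. For someone in control at rollover, the recorded time is the remaining time in control, given that control was present that day. For someone reaching control during the extension, it is the full time from onset. If relapse risk changes with time in control, these are different quantities, and the pooled median shifts with the proportion of each group as well as with the course of the disease on treatment.

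The SAP deals with this for neighbouring endpoints. For CR off oral corticosteroids (OCS), CR or PR off OCS, and CR on minimal OCS, participants already in the target disease status on day 1 of the treatment period are non-evaluable for that period. Time to relapse has no corresponding rule or separation.

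The protocol lists time to relapse as a secondary endpoint under long-term efficacy and durability of response, and its introduction says the study will evaluate whether long-term treatment can prevent relapse. A reader will want to know what the reported median is measured from.

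**Working it through.** **No planned figure to reproduce.** The documents give no sample size, expected median or relapse rate for this endpoint.

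**Step 1: the reset, from the text alone.** Take a participant who reached CR 20 weeks before rollover and relapses 10 weeks after it. Item 9 computes end date minus start date plus 1.
- From rollover, as the SAP has it: 10 × 7 + 1 = 71 days.
- From onset: 30 × 7 + 1 = 211 days.

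A participant who reaches CR at extension week 4 and relapses 10 weeks later is also recorded at 71 days, but there it is the full time from onset.

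**Step 2: why the direction depends on the hazard.** Let S(t) be the relapse-free proportion from onset. For someone already in control for a days, the SAP clock estimates S(a + t)/S(a). As an assumption, take Weibull times with shape k and S(182 days) = 0.50. Then S(a + 182)/S(a) = 0.50^d, with d = ((a + 182)/182)^k − (a/182)^k. For a = 140 days:
- k = 0.6 (falling hazard): d = 1.408 − 0.854 = 0.554, giving 68%.
- k = 1 (constant): d = 1.769 − 0.769 = 1.000, giving 50%.
- k = 1.5 (rising): d = 2.353 − 0.675 = 1.679, giving 31%.

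The same rule puts this subgroup above, at or below the 50% that applies from onset.

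**Step 3: the pooled curve.** This was simulated with 400,000 participants per scenario. Follow-up of 56 weeks comes from the documents. Everything else is assumed: 30, 60 or 90% in control at rollover; their onset uniform over the preceding 0 to 224 days, with no relapse between onset and rollover; onset in the others uniform over extension days 14 to 112. The true median from onset is 182 days.

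| Hazard | Pooled 26-week relapse-free (truth 50%), at 30 / 60 / 90% in control at entry | Pooled median, days |
|---|---|---|
| Falling (k = 0.6) | 54.4 / 58.5 / 62.9% | 222 / 265 / 310 |
| Constant (k = 1) | 50.0 / 49.9 / 50.0% | 182 / 182 / 182 |
| Rising (k = 1.5) | 46.0 / 42.0 / 38.0% | 168 / 154 / 140 |

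With a truth of 70%, the pooled estimates are 73.0 / 75.9 / 78.8%, 70.0 / 70.1 / 70.0% and 66.5 / 63.3 / 59.8%. Unless the hazard is constant, the result moves with the entry mix alone.

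**Step 4: backdating the origin.** Counting from true onset, with participants joining the risk set only at rollover (delayed entry), gave 50.0 to 50.3% (truth 50%) and 69.8 to 70.3% (truth 70%). Counting from true onset without delayed entry gave 55.6 to 76.4% against 50%, too high in all nine scenarios, because it credits time in which relapse could not be observed.

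**The case against.** The strongest reply is that the rule is a coherent extension-period origin, that nobody has shown it misleads, and that the endpoint is descriptive. Several parts of this stand.

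- **Direction.** A reader might infer that the curve overstates durability, since participants in control at rollover look like survivors. The documents do not support this. They contain no information on the shape of the relapse hazard. They also give reasons why it could rise during the extension: OCS tapering continues, several rescue therapies are stopped at once, and before amendment 2 efgartigimod itself was stopped on sustained CR or PR.
- **Size.** One can produce an apparent optimism of 6 to 14 points for participants in control at entry by assuming varying risk between people (mean relapse hazard 0.02 per week, gamma frailty variance 0.5 to 2) and entry only if relapse-free since first control. That frailty model can only give a falling population hazard. The entry condition is not the trial's: Protocol section 5.1 requires completion of the week 36 visit, section 4.2 admits participants who needed rescue therapy, and relapse and treatment failure are listed baseline statuses. If parent-study relapsers are instead assumed to regain control after 3 to 12 weeks, with no dropout, the same model gives pooled values of 65.0, 67.5 and 71.4% at 24 weeks, against 65.0, 67.5 and 71.5% from onset. The pooled bias is then about nil, because each person's own hazard is constant and everyone contributes one observation. Incomplete recovery or selective dropout would bring some bias back.
- **Backdating.** For parent-study placebo participants, an origin in ARGX-113-2009 would put time without efgartigimod on the clock. The SAP says the baseline value is copied into the extension database; it does not say that earlier onset dates are.
- **Mitigation.** Baseline status is tabulated, and disease status and time to relapse are listed by participant, so the split could be rebuilt by hand.

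None of this gives the pooled median a single origin. A split recoverable only from listings does not help a reader of the table.

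**Conclusion.** The mixed origin follows directly from items 8 and 9 and SAP Table 2, and it needs no assumption beyond some participants entering in CDA, CR or PR. The pooled Kaplan-Meier median therefore has no single interpretation.

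The bias relative to time from onset is of unknown sign and size: upward if the relapse hazard falls with time in control, downward if it rises, about nil if it is constant. In the scenarios above with a true value of 50%, the departures ran from 12 points low to 13 points high at 26 weeks. They rest on assumed hazard shapes, entry mixes and onset times and illustrate the possible range; they do not predict the result. A claim that the analysis overstates durability, or by how much, goes beyond the documents.

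As the endpoint is secondary and descriptive, this is an inexpensive improvement to interpretability and not a threat to the study's conclusions.

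**What to change.** In SAP section 4.1.2 item 9 and Table 14.2.1.8, keep the pooled row if wanted and add two Kaplan-Meier rows:

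1. In CDA, CR or PR on day 1 of the evaluation period. Label the time as running from the start of that period, which is rollover when it is the participant's first phase.
2. CDA, CR or PR reached during the evaluation period. Label the time as running from onset.

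Classify by the disease status on day 1; for first-phase entrants this is the baseline status already collected. Show the number of participants and events in each row, and state the origin in a footnote.

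The cost is one derived flag and fewer participants per row, so medians will be less precise and may not be reached.

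Onset dates from ARGX-113-2009 should be used only as an optional sensitivity analysis, and only if those dates prove to be available. It should always use delayed entry at rollover and show parent-study placebo participants separately.
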